5.1.2 Consent Process

Upon contacting the DHOs' offices, the SPIRIT Uganda PI or Project Coordinator will describe the SPIRIT trial, and screen for enrollment. All eligible DHOs and/or District TB Supervisors (or other DHO-appointed TB focal person) that agree to participate will provide written consent prior to randomization. If a DHO or TB supervisor departs for a new position, we will consent the incumbent DHO or TB supervisor for study participation.

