4 Secondary outcome: Knowledge, attitudes, and practices regarding IPT

To assess mechanisms through which the intervention operates, we will conduct annual quantitative surveys among DHOs and DTLSSs to evaluate changes in their knowledge, attitudes, and practices regarding IPT. Details of these surveys are available elsewhere; here, we focus on the statistical analysis to evaluate change from baseline in familiarity with IPT, knowledge of IPT's health benefits, and practical challenges in TB management. Specific survey questions and their coding are given

in the Appendix.

Data source: Surveys will be administrated to all DHOs and DTLSSs by study staff at the time of randomization and then 1 and 2 years later. Study staff will attempt to reach and survey all participants in both arms.

As an example of a question, consider “*On a scale of 1 to 5, with 5 being very familiar with IPT, and 1, not knowing much yet about IPT, how familiar are you with IPT?*” The possible answers are “1: No knowledge of IPT; 2: Somewhat unfamiliar–low knowledge of IPT; 3: Somewhat familiar; 4: Familiar; 5: Very familiar–high knowledge of IPT”. Thus, the survey questions will elicit Likert-type answers with evenly spaced responses. In line with standard practice for such outcomes , we will evaluate them quantitatively. Specifically, for each district, we will calculate the average response among its representatives at baseline, at year-1, and at year-2.

Effect estimation: To estimate and obtain inference for the effect of the SEARCH-IPT intervention on IPT knowledge/attitudes/practices, we will first calculate a change-outcome as the average response at follow-up minus the average response at baseline in each district. We will then compare these outcomes with the unadjusted effect estimator (equivalent to the Student’s *t*-test) and test the *null hypothesis* of no improvement in IPT knowledge/attitudes/practice, as compared to standard-of-care, with a one-sided test at the 5% significance level.

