We will focus on effect measures on the absolute scale and for the N districts with both baseline and follow-up data. Primary analyses will focus on the change from baseline to year-1. Secondary analyses will focus on change from baseline to year-2 and from year-1 to year-2. We will report point estimates and two-sided 95% confidence intervals for the arm-specific annual responses, the arm-specific estimates of change, and the effect estimates. Primary analyses will weigh the N districts equally and include all districts, including those created during follow-up. We will use the same approach to statistical inference as the primary endpoint.

Additional analyses: We will repeat the above analyses stratifying on whether the respondent is a DHO or a DTLSS.

5 Secondary outcome: IPT completion among persons starting IPT

A key intermediate between IPT uptake and TB prevention is IPT completion. Therefore, we will also assess the SEARCH-IPT intervention on “IPT completion”, defined as dispensation of a full course of IPT within 9 months of initiation. As detailed in the corresponding SOP, this endpoint will be measured among $N = 800$ (400 persons/arm) who are aged 15+ years, HIV-infected, and started IPT at one of 16 facilities in Southwestern region. Within each clinic, these participants will be sampled such that half initiated IPT before Q3-2019 and half initiated in Q3-2019 (during the “100-day IPT push”).

Data source: For each sampled participant, de-identified data on IPT completion (via INH pills dispensed over 9 months) will be obtained from the IPT register and blue cards. Additionally, data on the following variables will be recorded: gender, date of birth, marital status, ARV regimen, ARV switches while on IPT (date and new regimen), most recent HIV RNA viral load, if on Septrin or Dapsone while taking INH, and diagnosis of active TB.

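### The survey change score averages whoever answers at each wave, so losing one of a district's roughly two officers shifts its change by half the gap between roles although nobody changed

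*SAP*

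**What the plan says.** SAP Section 4 sets out to "evaluate changes in their knowledge, attitudes, and practices regarding IPT" among DHOs and DTLSs, with surveys at randomization and one and two years later. At each wave "for each district, we will calculate the average response among its representatives at baseline, at year-1, and at year-2". The outcome is then a "change-outcome as the average response at follow-up minus the average response at baseline in each district". Arms are compared without adjustment in a one-sided 5% test; the primary contrast is baseline to year 1.

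On who answers, Section 4 says only that "Study staff will attempt to reach and survey all participants in both arms". Sections 2 and 3 of the SAP each have a missing-data paragraph; Section 4 has none. Protocol 5.1.2 enrols "All eligible DHOs and/or District TB Supervisors (or other DHO-appointed TB focal person) that agree to participate", so a district may have two respondents or one. It adds: "If a DHO or TB supervisor departs for a new position, we will consent the incumbent DHO or TB supervisor for study participation".

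Section 4 repeats the analysis separately for DHOs and DTLSs, under additional analyses.

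On which districts count, Section 4 first defines effects "for the N districts with both baseline and follow-up data", and then says: "Primary analyses will weigh the N districts equally and include all districts, including those created during follow-up".

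**The concern.** The score is a difference between two district averages, not an average of differences within a post. The two averages need not cover the same posts. A DHO is a general health manager and a DTLS is a TB specialist, so their answers on isoniazid preventive therapy may well sit at different levels. If both answer at baseline and one is not reached at year 1, the role difference enters the change score.

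This outcome is meant to show how the intervention works. With loss equal across arms, the effect is extra variance in a comparison with few independent units. With loss that differs by arm and role, it is a bias whose direction depends on which role is lost.

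The two statements on district inclusion are a smaller matter. A district that did not exist at randomization cannot have its own baseline-to-year-1 change.

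**Working it through.** The documents give no power, response or turnover figure for the survey, so there is no stated figure to reproduce. The check is algebra plus assumed inputs, marked as such.

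**One district.** Let the DHO score *a* and the DTLS score *b*, with no change in either. The baseline mean is (a + b)/2.
- DHO missing at follow-up: change = b − (a + b)/2 = (b − a)/2.
- DTLS missing at follow-up: change = (a − b)/2.
- Scores 3 and 5: baseline 4.0. With the DTLS alone at year 1 the mean is 5.0, change +1.0; with the DHO alone, −1.0.
- Scores 3 and 4: ±0.5. The largest possible shift on the 1 to 5 scale, from scores 1 and 5, is ±2.0.

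**Arm contrast.** Let g be the mean gap (DTLS minus DHO), and let mI and mC be the shares of intervention and control districts losing a given role at follow-up. With no true change, the expected contrast (intervention minus control) is (mI − mC) × g/2 if the DHO is lost, and the negative of that if the DTLS is lost. Assume mI = 0.05 and mC = 0.20:
- g = 1: 0.15 × 0.5 = 0.075 points.
- g = 2: 0.15 × 1 = 0.15 points.
- Equal shares: 0.

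**Noise with equal loss.** Assume between-person SD 1.0, within-person SD 0.5 at each wave, and 20% of districts losing one role.
- No loss: variance of district change = (2 × 0.25)/2 = 0.25, SD 0.50.
- A district that lost a role, planned score: (1 + 1)/4 + 0.25 × 1.5 = 0.875.
- Planned score overall: 0.8 × 0.25 + 0.2 × 0.875 + 0.2 × 0.8 × g²/4 = 0.375 + 0.04g². The SD is 0.61 (g = 0), 0.64 (g = 1) or 0.73 (g = 2).
- Within-role change: 0.8 × 0.25 + 0.2 × 0.5 = 0.30, SD 0.55 whatever g is.

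**Test behaviour under the plan's inference.** Section 4 adopts the primary endpoint's inference: 7 intervention clusters and 40 control districts as independent units, hence 47 − 2 = 45 degrees of freedom. The simulation used the same SDs, 20% control against 5% intervention loss, an assumed 40 intervention districts and no true change. One-sided rejection at nominal 5% was:

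| Role lost | Gap 1 | Gap 2 | Within-role score |
|---|---|---|---|
| DTLS (assumed higher scorer) | about 14% | about 25% | about 5% |
| DHO | about 1.7% | about 0.5% | about 5% |

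These rates move by a point or two with the exact form of the standard error.

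**District inclusion.** The baseline survey was at randomization. The SAP study timeline ties the Q1/Q2-2019 start of follow-up to the first-year meeting, which puts randomization about a year earlier, and it places the division of districts in 2019. A new district therefore has no baseline of its own, and Section 4 gives no rule assigning it the parent district's.

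**The case against.** **Replacement of officers.** A reader might infer that any turnover makes the change score spurious. The documents do not support that. The outcome is defined per district, and Protocol 5.1.2 deliberately brings in the new post-holder. If the target is the knowledge of whoever holds the post, a successor's answer belongs in it. The SAP's reference to officers' own change does not settle the matter. Non-response by one of two officers remains a problem on either reading.

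**Differential loss by arm.** It is tempting to infer that control officers, who have no mini-collaboratives, will be harder to reach. Nothing in the documents shows this. Protocol Table 2 schedules contact with control DHOs and TB staff at baseline and at 12, 24 and 36 months, and Section 4 promises equal effort in both arms. The rejection rates above illustrate a mechanism; they are not the plan's error rate.

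**Existing safeguard.** The analysis by role already gives within-role change, free of this mixing. That stands as a partial answer, but the main survey test uses the mixed mean.

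**New districts.** A district with no baseline has no change score and drops out, so no baseline-to-year-1 estimate is altered. The year-1-to-year-2 contrast could include a new district surveyed at both waves. Survey details are said to be held elsewhere, so a linkage rule may exist there.

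**Phase 2.** A reader might carry the point over to the District Health Team scores. Protocol 10.5 defines no district average by wave, so the documents do not support that.

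**Conclusion.** The concern holds for one-officer non-response. The planned score has no same-post condition, and losing one of two roles shifts a district's change by exactly half the role gap. The consequence that does not need loss to differ by arm is noise: with 20% loss in each arm and the assumed SDs, the SD of district change is 0.61 to 0.73, against 0.55 for within-role change. Bias requires loss by role that differs between arms and a gap between roles. Assuming 20% against 5% and a gap of 1 to 2 points, it is 0.075 to 0.15 points, with the sign set by the role lost. Neither the loss rates nor the gaps are documented.

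The conflict over new districts is one of wording and should be reconciled. The documents support neither a finding that the survey result is biased nor one that replacing officers is an error. This is a cheap improvement to a secondary outcome and does not touch the primary endpoint.

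**What to change.** For the main survey test, compute change within role: the same post at follow-up minus that post at baseline, for DHO and DTLS separately. Average whichever role-specific changes are available in each district. Count a replacement in the same post as that role, and add a sensitivity analysis limited to the same individual at both waves. Report response by role, wave and arm.

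Replace the two inclusion statements with one: contrasts from baseline use districts with both waves, or state an explicit rule giving a new district its parent's baseline. The year-1-to-year-2 contrast may include a new district surveyed at both.

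Version 2.0 was locked before unblinding of the survey outcomes and version 2.1 before manuscript submission (SAP 6.1). Present this as a dated, labelled addition beside the planned score.

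The cost is a few sentences and a few lines of code, since the planned stratification already needs respondent role. There are two downsides: a district with no role observed at both waves drops out, and if true change differs between roles, some mixing remains when a role is missing.

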Statistical inference: Recall that 4-7 districts were put into groups for the purposes of pair-matching and treatment randomization. In the intervention arm, these clusters are the basis for mini-collaborative activities. In the control arm, there are **no** mini-collaborative meetings or any other study activities. Instead, the control condition corresponds with the standard of care. Therefore, it is reasonable to assume districts in the control arm are independent.

Given this independence structure (at the mini-collaborative level in the intervention arm and at the district level in the control arm), we take the following approach to statistical inference. In the primary analysis, we will assume there are 7 independent units corresponding to the mini-collaboratives in the intervention arm, and 40 independent units corresponding to the districts in the control arm (total $N = 47$). In sensitivity analyses, we will treat the randomized cluster as the independent unit (total $N = 14$). In all analyses, we will use the influence function for standard error estimation [11] and the Student's t -distribution with $(N - 2)$ degrees of freedom as finite sample approximation to the standard normal distribution [11].

Primary analyses will break the matched pairs used for randomization. For completeness, we will also conduct a paired t-test ($N = 7/\text{arm}$), implement a permutation test, and also estimate the intervention effect with mixed (random) effects models and with generalized estimating equations (GEE) [13, 14].

Sensitivity analyses: In addition to the sensitivity analyses described above, we will conduct the following sensitivity analyses. To minimize the impact of secular trends, we will exclude the “100-day IPT push” (Q3-2019). To better understand the impact the COVID-19 pandemic which caused a lockdown to be initiated in Q2-2020, we will conduct an analysis excluding the post-lockdown period and an analysis excluding the pre-lockdown period. Given the expected skewed distribution of clinic sizes, we will conduct two sensitivity analyses excluding clinics with baseline active care size exceeding 2500 patients and exceeding 5000 patients.

Subgroup analyses: We will repeat the above analyses within strata defined by sex, baseline active care size (≤ 1000 vs. >1000), and region.

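### The knowledge and attitude survey scores are compared only as unadjusted change scores; adjusting for the baseline score already collected would usually be more precise, by an amount the documents do not fix

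*SAP*

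**What the plan says.** SAP section 4 (Effect estimation) defines the outcome: "we will first calculate a change-outcome as the average response at follow-up minus the average response at baseline in each district". It will then "compare these outcomes with the unadjusted effect estimator", which it equates with Student's t-test, and test each item "with a one-sided test at the 5% significance level".

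The baseline score exists: "Surveys will be administrated to all DHOs and DTLSSs by study staff at the time of randomization and then 1 and 2 years later". The effect is defined "for the N districts with both baseline and follow-up data", on the absolute scale. The primary contrast is baseline to year 1. Baseline to year 2 and year 1 to year 2 are secondary. No adjusted analysis of these scores is named at any level.

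Section 4 adds: "We will use the same approach to statistical inference as the primary endpoint". For the primary endpoint (SAP section 2, Statistical inference) the intervention arm counts as 7 units, one per mini-collaborative. The control side is treated differently, as "40 independent units corresponding to the districts in the control arm". Standard errors come from the influence function, with a t reference on N − 2 degrees of freedom. A sensitivity analysis uses the 14 randomized clusters. That text settles units, standard errors and degrees of freedom. It does not replace the estimator that section 4 names.

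SAP sections 2 and 3 let TMLE choose among the baseline value of the outcome, baseline active care size and no adjustment, with the unadjusted estimator as secondary. Section 5 adjusts IPT completion for individual covariates. The surveys are the only one of the SAP's four outcomes without an adjusted analysis, and no reason is given.

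**The concern.** Subtracting the baseline score fixes its coefficient at 1. If the true slope of follow-up on baseline is below 1, subtraction over-corrects and puts baseline noise into the outcome. A slope below 1 is plausible here. The outcomes are single five-point items averaged over a district's few representatives. Officers who leave are replaced by incumbents (Protocol 5.1.2), so the two surveys may reach different people.

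These surveys are meant to show how the intervention works. No power is stated for them, and the primary inference counts only 7 independent intervention units. Precision that can be had from data already collected is worth taking.

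**Working it through.** **Nothing to reproduce.** The only power calculation in the SAP (Appendix 6.3) is for the uptake rate. No document gives an SD, correlation, effect size or power for the survey scores.

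**Inputs.** Units: 7 + 40 in the primary inference and 7 + 7 in the sensitivity analysis (SAP section 2). The number of control districts with both surveys may be below 40. Assumed: r from 0.3 to 0.7, equal SDs in the main case, and equal variance for all units (a simplification, since an intervention unit pools several districts).

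**Formulas**, with s0 and s1 the baseline and follow-up SDs:

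- Var(change) = s0² + s1² − 2·r·s0·s1
- Var(adjusted) = s1²(1 − r²)
- Difference = (s0 − r·s1)², which is never negative and is zero only when the slope r·s1/s0 equals 1

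With s0 = s1 = s these become 2s²(1 − r) and s²(1 − r²). Their ratio (adjusted over change) is (1 + r)/2, so the precision lost is (1 − r)/2. Estimating the slope multiplies the adjusted variance by about (N − 3)/(N − 4): 44/43 = 1.023 for N = 47 and 11/10 = 1.10 for N = 14.

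**Precision lost by the change score, equal SDs:**

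| r | Large sample | 7 + 40 units | 7 + 7 units |
|---|---|---|---|
| 0.3 | 35% | 1 − 0.65 × 1.023 = 33.5% | 1 − 0.65 × 1.10 = 28.5% |
| 0.5 | 25% | 23.3% | 17.5% |
| 0.7 | 15% | 13.0% | 6.5% |
| 0.8 | 10% | 7.9% | 1.0% |
| 0.9 | 5% | 2.8% | −4.5% |

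A simulation with 20,000 replicates per setting agreed for r = 0.3, 0.5 and 0.7: 32.7%, 22.6% and 13.3% with 7 + 40 units; 28.7%, 17.8% and 6.4% with 7 + 7.

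**Unequal SDs, large sample, r = 0.3 to 0.7.** Let q = s1/s0. The loss is 1 − q²(1 − r²)/(q² + 1 − 2rq).

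- q = 0.8 (for example, follow-up scores bunched at the top of the scale): 1 − 0.5824/1.16 = 49.8% at r = 0.3, and 1 − 0.3264/0.52 = 37.2% at r = 0.7.
- q = 1.25: 1 − 1.4219/1.8125 = 21.6% at r = 0.3, and 1 − 0.7969/0.8125 = 1.9% at r = 0.7.

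**What this means in use** (large sample, equal SDs, r = 0.3, 0.5, 0.7). The change-score standard error is 24%, 15% and 8% wider than the adjusted one. If the change score had 80% power (one-sided 5%, normal approximation), adjustment would give about 92.5%, 89% and 85%.

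**The case against.** The strongest reply is that the change score follows the stated objective. Protocol 5.6.1 defines this secondary outcome as change over time, compared across arms, and subtraction does use the baseline. The uptake and TB rates have no baseline subtracted, so the contrast with SAP sections 2 and 3 is less sharp than it looks. That is fair, but it does not defend leaving adjustment out. In a linear model, adjusting the change score for baseline gives the same treatment effect as adjusting the follow-up score, so the change-scale question is unchanged.

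A second reply is that the gain is uncertain and not free. This stands. With 7 + 7 units the gain is about 1% at r = 0.8 and is reversed at 0.9. At r = 0.7 with q = 1.25, the variance ratio is 0.981 × 1.10 = 1.08, so adjustment does slightly worse. Keeping no adjustment among the candidates limits this risk.

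A reader might infer that regression to the mean biases the effect. The documents do not support that: over randomization the change-score contrast is unbiased, and chance baseline imbalance is already counted in the variance ratio. It should not be counted as a second harm.

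Nor do the surveys carry the whole question of mechanism. Mediation by participation (SAP section 2), provider surveys and qualitative work (Protocol 5.6.1 and 5.6.2) and fidelity measures (Protocol 5.6) also bear on it.

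**Conclusion.** The point holds as one of efficiency on a secondary outcome. The SAP plans only an unadjusted change-score comparison where a baseline-adjusted one is available without losing a district, and in large samples the change score is never the more precise of the two.

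It is tempting to state the loss as a flat 15% to 35%. The documents do not support that as a fact about this trial, because it needs an assumed r of 0.7 to 0.3, equal SDs and large samples. With equal SDs and the same r, the loss is about 13% to 33% at 7 + 40 units and about 6% to 28% at 7 + 7. In large samples it ranges from about 2% to 22% if the follow-up SD is 1.25 times baseline, and from 37% to 50% if it is 0.8 times. The validity of the planned test is not in question on this ground.

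**What to change.** For the baseline to year 1 and baseline to year 2 contrasts, add the district's baseline average score as an adjustment candidate, with no adjustment retained, in the TMLE used for the primary endpoint. A linear covariate would also do. Keep the absolute scale, the independent units and the analysis set. Report the unadjusted change score as secondary.

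Treat the year 1 to year 2 contrast separately. The year-1 score is measured after randomization and should not be an adjustment variable. Use only the score from randomization, or leave that contrast unadjusted.

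The cost is a short addition to SAP section 4 and one degree of freedom, with no new data. Timing matters: version 2.0 was locked before the survey outcomes were unblinded, and version 2.1 is described as correcting only grammar and typos (SAP Appendix 6.1). If the survey data are already unblinded, the adjusted analysis must be labelled post hoc.

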6.5.2 Analysis

6.5.2.1 IPT completion:

Primary outcome: We will examine INH completion, defined as an indicator of dispensation of 180 pills of INH within 9 months of INH initiation, as the primary outcome of Aim 2 among sampled patient charts in intervention and control groups (see Section 6.5.3. below). The effect of SPIRIT on INH completion will be

[figure not shown]
estimated with TMLE, analogously to the primary endpoint of IPT uptake (see Section 5.7 above). We will account for clustering by randomization group and by DHO within randomization group. In all analyses, we will adjust for the sampling probability to make inferences about the target population of IPT-prescribed, HIV-infected persons in Uganda.

Figure 3 shows the effect size that we are powered to detect when IPT completion (as measured by hair levels) is 30-50% in the control arm. These calculations assume 30-40 patients sampled per DHO group, 12 DHO groups per arm, and a matched pair coefficient of variation $k_m=0.2$. Assuming IPT completion is 44% under the standard of care, we anticipate at least 80% power to detect a 40% increase in IPT completion due to the SPIRIT intervention (Figure 3).⁴⁴

Additional secondary analyses: We will examine the effect of SPIRIT on ART adherence and viral suppression in the sub-sample of patients for Aim 2.

Qualitative analysis: Data collection and analyses will be similar to those described for Aim 1.

Figure 3 (right): Effect size (in percent increase in IPT completion) detected with at least 80% varying the completion under the standard of care (SoC) and number of patients sampled per DHO group. We assume 12 DHO groups per arm and a matched pair coefficient of variation $km=0.2$.

[figure not shown]
6.5.2.2 TB incidence:

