Effect estimation: When evaluating IPT completion among the subsample of initiators, we will evaluate the arm-specific and relative risk of IPT completion with an individual-level TMLE, adjusting for sex, age, and timing of IPT initiation. The details of this approach are given in van der Laan et al. [16]. In brief, this approach assumes the adjustment covariates are sufficient to “block” the impact of shared factors that may differ between clusters, here clinics. In other words, two participants from two different clinics would have the same outcome probability if they had the same gender, age, and IPT initiation date *and* their respective clinics had received the same level of the treatment. This approach also relies on the assumption that sampled participants are conditionally independent, given the treatment assignment and the adjustment set. These assumptions are reasonable given that, beyond the intervention, the major driver of IPT prescribing practices and, thus, completion are secular factors (e.g., the Q3-2019 “100-day IPT push”) and the participant’s timing of IPT initiation is included in the adjustment set.

To flexibly control for sex, age, and timing of IPT initiation, we will implement TMLE with Super Learner, an ensemble machine learning algorithm that creates the best weighted combination of predictions from a set of candidate learners [17]. Our candidates will include multivariate adaptive regression splines, main terms logistic regression, and the simple mean. In sensitivity analyses, we will implement TMLE using main terms logistic regression instead of Super Learner. Additional sensitivity analyses will include marital status in the adjustment set and include penalized regression in the Super Learner library.

We will also evaluate IPT completion using an analogous analysis as for the primary endpoint. Specifically, treating the clinic as the independent unit, we will use adaptive pre-specification to select among the following individual-level adjustment variables the ones that maximize precision in TMLE: sex, age, and timing of IPT initiation [5, 18]. We will also report unadjusted estimates from this approach as well as conduct an analysis weighting proportionally to the clinic’s total IPT starts and an analysis treating clinics as fixed effects.

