For all approaches, we will test the *null hypothesis* of no improvement from the intervention with a one-sided test at the 5% significance level. We will also report point estimates and two-sided 95% confidence intervals for the relative effect, the absolute effect, and the arm-specific mean outcomes. We will also report total completions by arm.

Additional analyses: We will repeat the above analyses within subgroups defined by sex, timing of IPT initiation (before Q3-2019 “100-day IPT push” or during Q3-2019), age group (15-24 years or 25+ years), and marital status (never married, married/living together, divorced/separated/widowed, missing). We will also use an individual-level TMLE to examine predictors of non-completion. We will provide descriptive statistics on the subsample, including their demographics and care outcome (e.g., ARV switches).

Secondary endpoint: We will repeat the above analyses to examine the effect of the SEARCH-IPT intervention on viral suppression, defined as HIV RNA viral level <400 copies/mL.

6 Appendix

6.1 History of changes:

- Version 1.0 was locked on July 18, 2021 prior to unblinding and effect estimation for IPT uptake (the primary outcome), IPT completion among persons starting IPT, and HIV-associated TB incidence.
- Version 2.0 was created to include the pre-specified analysis plan for the quantitative surveys on knowledge, attitudes, and practices regarding IPT. Version 2.0 was locked on September 15, 2021, prior to unblinding and effect estimator for the survey outcomes.
- Version 2.1, this version, was created to correct grammatical errors and other typos. Version 2.1 was locked on November 10, 2021 prior to submission of the manuscript.

6.2 Select survey questions:

[figure not shown]
The following are examples of survey questions, designed to understand the impact of the SEARCH-IPT intervention on IPT knowledge, attitudes, and practices among DHOs and DTLSSs. Full survey materials are available elsewhere.

1. How familiar are you with IPT? With responses: 1: no knowledge of IPT; 2: somewhat unfamiliar – low knowledge of IPT; 3: somewhat familiar; 4: familiar; 5: very familiar – high knowledge of IPT.
2. How strong is the evidence that INH prevents active TB in HIV-infected patients? With responses: 1: very weak; 2: weak; 3: mixed; 4: strong; 5: very strong.

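### IPT completion: the leading analysis treats 800 people from 16 clinics as independent, contrary to the protocol's clustering rule; no analysis is named as deciding and none uses the randomised group

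*SAP*

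**What the plan says.** Protocol 6.5.2.1 plans a TMLE of completion on the model of the primary endpoint and adds: "We will account for clustering by randomization group and by DHO within randomization group". Its power statement takes the DHO group as the unit.

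SAP Section 5 samples 400 people per arm who "started IPT at one of 16 facilities in Southwestern region". Within each clinic they are "sampled such that half initiated IPT before Q3-2019 and half initiated in Q3-2019". The first analysis described is an individual-level TMLE adjusted for sex, age and timing of initiation, of which the SAP says: "This approach also relies on the assumption that sampled participants are conditionally independent, given the treatment assignment and the adjustment set". It defends this by arguing that, beyond the intervention, secular factors drive prescribing and completion, and that timing is in the adjustment set.

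The SAP then adds an analysis "treating the clinic as the independent unit", with unadjusted, weighted and clinic fixed-effect versions. The one-sided 5% test is common to them: "For all approaches, we will test the" null hypothesis of no improvement. The same analyses are repeated for viral suppression.

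For the primary outcome, SAP Section 2 places independence "at the mini-collaborative level in the intervention arm and at the district level in the control arm", and adds: "In sensitivity analyses, we will treat the randomized cluster as the independent unit". SAP Sections 3 and 4 carry that approach over to TB incidence and the surveys. Section 5 does not.

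**The concern.** The protocol and SAP give different rules for one outcome, and the history of changes in SAP Appendix 6.1 does not declare the departure.

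The SAP's defence of independence is weak given its own sampling. The before/during Q3-2019 split is fixed at half and half in every clinic, so adjusting for it cannot remove differences between clinics, districts or groups. Completion is measured by pills dispensed. The protocol names influences on dispensing that act above the individual: district requests for INH (5.5), facility stock-outs (Table 1), and refill strategies, including 90-day against 30-day supply, that the collaboratives may develop (5.3.2). None is in the adjustment set.

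If such influences leave residual variation between clinics or groups, the individual-level interval is too narrow and its test exceeds 5%. With no deciding analysis named, a reader cannot tell whether that interval or the wider clinic-level one supports the conclusion. The SAP itself describes completion as a key intermediate between uptake and TB prevention.

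**Working it through.** **1. The protocol's own figure.** Inputs from 6.5.2.1: p0 = 0.44, a 40% relative increase (p1 = 0.616), k_m = 0.2, 12 groups per arm, m = 30 to 40 people per group. Matched-pair formula, two-sided 5%, 80% power:

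c = 2 + (1.96 + 0.84)² × [p0(1−p0)/m + p1(1−p1)/m + k_m²(p0² + p1²)] / (p1 − p0)²

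- m = 30: c = 11.89; power with 12 groups is 80.4%.
- m = 40: c = 10.87; power with 12 groups is 84.5%.

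The stated power of at least 80% is reproduced. It rests on clustering by DHO group and on 12 groups per arm. Protocol 9.2.1 puts 2 intervention and 2 control groups in the Southwest.

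**2. Assumptions for the SAP design.** 800/16 = 50 people per clinic; 800/4 = 200 per group; 44% completion; k = 0.05, 0.1 or 0.2. The protocol's 0.2 was a matched-pair value for a different design and for completion measured by hair levels, so I treat it as an upper end.

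Three placements of the residual variation:
- A: between clinics.
- B: the SAP Section 2 structure, with 2 mini-collaboratives in the intervention arm and independent clinics in the control arm (about one clinic per district).
- C: between groups in both arms.

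**3. Individual-level test.** ICC = (k·p)²/[p(1−p)]; for example, at k = 0.2, 0.088²/0.2464 = 0.0314. Design effect DE = 1 + (m − 1)·ICC, with m = 50 for A and m = 200 for C; B is the mean of the two arms. One-sided error = 1 − Φ(1.645/√DE). Coverage of the 95% interval = 2Φ(1.96/√DE) − 1.

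| k | ICC | DE A / B / C | Error A / B / C | Coverage A / B / C |
|---|---|---|---|---|
| 0.05 | 0.0020 | 1.10 / 1.24 / 1.39 | 5.8 / 7.0 / 8.2% | 93.9 / 92.1 / 90.3% |
| 0.1 | 0.0079 | 1.39 / 1.97 / 2.56 | 8.1 / 12.1 / 15.2% | 90.4 / 83.7 / 77.9% |
| 0.2 | 0.0314 | 2.54 / 4.90 / 7.25 | 15.1 / 22.9 / 27.1% | 78.1 / 62.4 / 53.3% |

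**4. Clinic-level test (t, 14 df).** Simulated with 8 clinics per arm, 50 people each, normal cluster effects on the proportion, and at least 60,000 runs per setting.

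| k | A | B | C |
|---|---|---|---|
| 0.05 | 5.0% | 6.2% | 7.4% |
| 0.1 | 5.0% | 8.9% | 12.4% |
| 0.2 | 4.9% | 13.3% | 20.1% |

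It holds its level against clinic variation and only partly against group variation.

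**5. Price of the clinic-level interval.** Width ratio = √DE × t(0.975, 14)/1.96, with t = 2.145 and DE from A: 1.15, 1.29 and 1.74 at k = 0.05, 0.1 and 0.2. The individual-level half-width is 1.96 × √(2 × 0.2464/400) = 6.9 points; at clinic level it is 7.9, 8.9 and 12.0.

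**6. Could the randomised group be the unit?** With 2 groups per arm, 200 people each and k = 0.2, SE = √{[(0.2464 + 0.2365)/200 + 0.04 × (0.1936 + 0.3795)]/2} = 0.113. On 2 df (one-sided critical t = 2.92), power for 44% against 61.6% is about 28%. A re-randomisation test that keeps two pairs has 2² = 4 assignments, so its one-sided p cannot fall below 1/4.

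The count of four groups is itself uncertain. Protocol 1.1 gives 14 Southwestern districts, but four groups of 4 to 7 need at least 16, and the 5 to 10 per group in protocol 9.2.1 would need at least 20.

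**The case against.** The SAP states its assumption openly and argues for it. It pre-specifies clinic-level analyses and reports intervals for every approach, so a reader will see the wider interval too. The order of presentation suggests that the individual-level TMLE leads. The adjustment is described at one point as using the initiation date, which can differ between clinics within the earlier half, so it may remove more than the before/during split does. The large error rates need k = 0.2, borrowed from another design; at k = 0.05 the error is 6% to 8%. The clinic-level test does not meet the protocol's rule either. Demoting a pre-specified analysis after lock could also look driven by results.

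Much of this stands as qualification. The residual variation is unknown, inflation is modest at the low end, clustering within clinics is partly covered, and the proposed remedy is partial. It does not remove the defect. Date, sex and age do not capture district supply, stock-outs or refill strategy. An implied order is not a named deciding analysis, and if the implied order is followed, the narrowest interval leads. The contradiction with the protocol is undeclared. The post-lock risk is a reason to date and explain the change.

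**Conclusion.** The concern holds and should be fixed. SAP Section 5 departs from the protocol's clustering rule without saying so, leaves the deciding analysis unnamed, and offers no analysis at the level that was randomised.

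The size depends on residual variation that the documents do not give. With 44% completion and equal clinic and group sizes, the individual-level test's true one-sided error runs from 6% (k = 0.05, between clinics) to 27% (k = 0.2, between groups), and coverage of its 95% interval from 94% down to 53%. Moving to the clinic level cures the first kind of variation and only part of the second. With about four groups, all in one region, the comparison can be no more than supportive and does not extend to Uganda as a whole, the target named in protocol 6.5.2.1.

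**What to change.** In SAP Section 5:

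1. Name the clinic-as-unit TMLE (t, 14 df), already planned, as the analysis that carries the conclusion for completion and for viral suppression.
2. Make the individual-level TMLE a sensitivity analysis, labelled as dependent on conditional independence.
3. Report the clinic ICC and the completion proportion in each randomised group.
4. State how many randomised groups contribute, that neither analysis accounts for group-level correlation, and that the result is therefore supportive and limited to the Southwest.
5. Reconcile the section with protocol 6.5.2.1 and SAP Section 2, and record the dated change in Appendix 6.1.

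Weights for the before/during Q3-2019 split affect only the target population and are optional.

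The cost is wording and reordering, with no new data, plus the wider interval shown above. Version 1.0 was locked before unblinding and 2.1 before manuscript submission, so the change may fall after unblinding. The entry should say so, and both intervals should be reported side by side.
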